4.2. Handling of missing data

Power calculations revealed a sample size of 300 households per areas. To compensate for eventual dropouts, 375 households will be sampled during the baseline data collection.

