2.3 Project design

Research design

A randomized controlled trial (RCT) will be conducted in a rural area, following a cross-sectional baseline assessment on situational factors, water quality at the point of collection and point of use, WASH infrastructure, knowledge, attitude and practice as well as health indicators using standardized tools. The follow-up assessment will be conducted 1 year after the intervention (if funding is available a second follow-up assessment 2 years after the intervention might be implemented). One to one matching with the intervention area will be done for the selection of the control area.

The study will comprise of the following intervention schemes

	Baseline scenario	Intervention	Nr of households
Area A	PWS	HHH + S-CHL	375
Area B	PWS	HHH + HWTS	375
Area C	PWS	HHH	375
Area D (Control)	PWS	-	375

PWS is an area with the availability of a piped water supply scheme, that has not yet received the WARM-P training intervention

HHH: household hygiene intervention in accordance with the WARM-P training, but not establishing access to products for household water treatment

HWTS providing access to high quality products for household water treatment and safe storage, including training on adequate product operation and maintenance

S-CHL providing scheme-level chlorination

Conceptual Framework of the Study

The framework of the study is based on the assumption that improved access to safe drinking water together with adequate hygiene and sanitation conditions will improve children's health by reducing diarrhea incidence as well as the incidence of intestinal parasitic infections and therewith improve children's nutritional status.

The framework illustrates that to have a sustainable effect on children's health status a combination of WASH infrastructure improvement and education interventions should be

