4 STATISTICS AND METHODOLOGY

4.1. Statistical analysis plan

Descriptive statistics will be calculated to describe the characteristics of the population and the status of WASH indicators. Frequencies and percentage will be computed for categorical variables while means and standard deviations will be calculated for continuous variables. Positive cases identified during health screening will allow estimating point prevalence. Pearson's chi squared and Fisher's exact test will be applied for finding the association with the prevalence of diarrhea, intestinal parasites (single, multiple), nutritional disorders and risk factors. Means will be compared by student's t test or ANOVA. Repeated measures multiple regressions will be used to find an association between binary or continuous outcomes and adjacent variables. Logistic regression analysis will be used to compare repeated binary health outcomes per child in multiple groups. Univariate association between two binary variables will be assessed through 2X2 tables. Categorical variables will be compared using design based chi-square analysis. In all analyses, a p- value (threshold of significance) <0.05 will be considered statistically significant.

Sample size and power calculations using G*Power 3.1 revealed a sample size of 350 households in each group to detect a small effect between 4 groups with a correlation of 0.1 among repeated measures with 80% power and a one-tailed alpha of 0.05 (Erdfelder *et al.* 1996). A sample size of 300 households will be required to detect a small to medium effect in Cohen's f2 at one-tailed alpha of 0.05 and a statistical power of 95% with multiple linear regression and 15 predictor variables (Faul et al., 2009).

We will sample 375 households per study area, which will have the advantage to better balance potential design effects. The same sampling plan will be used during the follow up study in both beneficiary and control areas. In addition, a drop-out rate of 7% is being considered.

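### Sections 3.4, 4.1 and 4.2 of the protocol give sample-size statements that cannot be reconciled: 350 against 300 households per area, and two different accounts of what 375 allows for

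*Protocol*

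**What the plan says.** Section 4.1 reports two calculations.

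- A four-group repeated-measures calculation that "revealed a sample size of 350 households in each group to detect a small effect between 4 groups". Its other inputs are 80% power, a one-tailed 5% level and a correlation of 0.1 between a household's measurements. No outcome and no numeric effect size are attached.
- A regression calculation: "A sample size of 300 households will be required to detect a small to medium effect in Cohen's f2". Its inputs are 15 predictors, 95% power and, again, a one-tailed 5% level. It is not said whether 300 is a total or a figure per area.

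The section then sets 375 households per area, citing a better balance of design effects, and adds: "In addition, a drop-out rate of 7% is being considered". Its decision rule for all analyses is p < 0.05, with no sidedness stated.

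Section 4.2 states: "Power calculations revealed a sample size of 300 households per areas". It explains 375 as compensation for drop-outs and does not mention 350. Section 3.4 describes the oversampling for lost households as slight. Sections 2.3 and 3.1 give 375 per area and 1,500 in total.

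**The concern.** A reader cannot tell whether the trial needs 350 or 300 evaluable households per area, or what the difference between that number and 375 is for. This matters in practice. If follow-up ends with 300 households per area, section 4.2 would let that pass as fully powered, while section 4.1 would call it 50 short. The claimed room for design effects matters too: the interventions are delivered by area and chlorination works at the level of the water scheme, so some clustering is to be expected.

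**Working it through.** **Inputs.** From section 4.1: 4 groups, correlation 0.1, 80% power, alpha 0.05, 350 per group, 375 sampled, 7% drop-out; for the regression, 300 households, 15 predictors, 95% power. From section 2.3: two measurements (baseline and one year; a further one only if funded). From section 4.2: 300 per area. Assumed, because the protocol gives no number: a small effect is Cohen's f = 0.10 for four groups, or d = 0.2 for two arms. Households are treated as independent unless a design effect is stated.

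**1. What 375 can absorb**

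- From 350 with 7% loss: 350 × 1.07 = 374.5, so 375 was evidently meant to cover this loss. The exact inflation is 350/0.93 = 376.3, and 375 × 0.93 = 348.75.
- Room left for a design effect when 350 are needed: 348.75/350 = 0.996. There is none.
- From 300 with 7% loss: 300/0.93 = 322.6, so 323 would be enough.
- From 300 to 375 as drop-out cover only: 1 − 300/375 = 20% loss. That rate is written nowhere and does not fit 7%.
- From 300 with 7% loss and the remainder for clustering: 348.75/300 = 1.16. This is the only combination with any room for a design effect. It discards the 350 in section 4.1, and section 4.2 assigns the whole difference to drop-outs.

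**2. Trying to reproduce 350 per group**

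Noncentral F with N households in total, k = 4 groups and m = 2 measures:

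- Between-group test: λ = f²·N·m / (1 + (m − 1)ρ), with 3 and N − 4 degrees of freedom.
- Group-by-time test: λ = f²·N·m / (1 − ρ), with the same degrees of freedom.
- Time effect: the second λ, with 1 and N − 4 degrees of freedom.

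| Test | Total N for 80% power at f = 0.10 | Per group | Power at 350 per group, f = 0.10 | f giving 80% power at 350 per group |
|---|---|---|---|---|
| Between groups | 604 | 151 | 99.4% | 0.066 |
| Group by time | 495 | 124 | 99.9% | 0.059 |
| Time only | 356 | 89 | over 99.9% | 0.050 |

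Example, between groups: λ = 0.01 × 604 × 2/1.1 = 10.98, which gives 80% power.

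The between-group result depends strongly on f: 0.06 needs 418 per group, 0.065 needs 356, 0.07 needs 307, 0.10 needs 151. Other effect-size conventions for repeated measures, and a one-way ANOVA, give 274 to 275 per group at f = 0.10. No variant tried at 80% power and f = 0.10 gives 350 per group.

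**3. The 300 from the regression**

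For the overall F test with 15 predictors and 95% power, f² = 0.10 needs 292 in total and f² = 0.09 needs 323. A total of 300 solves to f² ≈ 0.097, which is compatible with the verbal description in section 4.1. Read as 300 per area and pooled (1,200), the detectable f² would be about 0.023. The figure therefore reads more naturally as a total, but the protocol does not say so.

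**4. Sidedness**

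Section 4.1 specifies "80% power and a one-tailed alpha of 0.05". An F test across four groups has no directional form, so one-tailed has no meaning there. It does matter for a comparison of one arm with control (two-sample t, noncentrality d·√(n/2)). At d = 0.2, 80% power needs 310 per arm one-sided or 394 two-sided. With 348 per arm:

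| Assumption | One-sided | Two-sided |
|---|---|---|
| d = 0.2 | 84% | 75% |
| d = 0.231 | 92% | 86% |
| d = 0.2, design effect 1.5 | – | 58% |
| d = 0.2, design effect 2 | – | 46% |

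d = 0.231 is the arm-versus-control difference that f = 0.10 implies when control differs from three equal arms: f = d·√3/4, so d = 0.10 × 4/√3.

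**The case against.** The best defence is that recruitment is unaffected. Every section that gives a number to be sampled says 375 per area, above both 300 and 350. The 7% rate agrees with 350 to 375 and with the slight oversampling of section 3.4, so the stray item could be just the one sentence in section 4.2. A shortfall of 1.25 households is rounding. All of that stands. It narrows the repair but leaves two conflicts: 300 against 350, and a claimed design-effect margin that the 7% loss has already used.

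Several stronger readings are tempting and are not supported:

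- A reader might infer that 350 is arithmetically wrong. The protocol never gives a number for the small effect, and f of about 0.06 to 0.07 yields 350. The figure cannot be reproduced, but it is not shown to be false. Nor does its closeness to the total of 356 prove that a total was mislabelled, because that total belongs to the time effect and not to a comparison of groups.
- A reader might infer that the trial is underpowered. At f = 0.10 with independent households, 350 per group exceeds what the four-group tests need. The 75% for a two-sided arm-versus-control test rests on an assumed d = 0.2, and a modestly larger d takes it above 80%.
- A reader might see a contradiction between one-tailed alpha and the p < 0.05 rule. That rule gives no sidedness, so this is an ambiguity.

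**Conclusion.** Wrong as written. Sections 4.1 and 4.2 differ by 50 households per area on what the power calculation requires, and they justify the same 375 on incompatible grounds (7% stated, 20% implied). On the 350 basis, drop-out alone takes 375 down to 348.75, so the statement in section 4.1 that 375 also helps with design effects fails on its own figures. These conclusions need no outside assumption.

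That 350 cannot be reproduced follows from the missing effect size. The size of the gap (151 or 124 against 350 per group) rests on f = 0.10, two measures and independent households. It would be too strong to say that the trial has no valid power at all: the documents support only that its power statement is inconsistent and cannot be verified.

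**What to change.** Replace the sample-size text of sections 4.1 and 4.2 with one statement, keeping 375 per area, that gives:

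- one drop-out rate; at 7%, about 348 evaluable households per area;
- the numeric effect size and the contrast it applies to;
- the sidedness of that test;
- an explicit assumed design effect;
- the resulting power or minimum detectable difference.

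Delete the sentence in section 4.2 that gives 300 per area. State in section 4.1 whether the regression 300 is a total. Drop the claim that 375 also absorbs design effects unless the restated figures show it. Bring section 3.4 into line with the chosen drop-out rate.

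The cost is protocol wording, with no extra households. The drawback is that the stated power may be less favourable once sidedness and a design effect are explicit.

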5 REGULATORY ASPECTS AND SAFETY

5.1 Local regulations / Declaration of Helsinki

This research project will be conducted in accordance with the protocol, the Declaration of Helsinki [3], the principles of Good Clinical Practice, the Human Research Act (HRA) and the Human Research Ordinance (HRO) [1] as well as other locally relevant regulations. The Project Leader acknowledges his responsibilities as both the Project Leader and the Sponsor.

5.2 Notification of safety and protective measures (HRO Art. 20)

The project leader is promptly notified (within 24 hours) if immediate safety and protective measures have to be taken during the conduct of the research project. The Ethics Committee will be notified via BASEC of these measures and of the circumstances necessitating them within 7 days.

5.3 Serious events (HRO Art. 21)

If a serious event occurs, the research project will be interrupted and the Ethics Committee notified on the circumstances via BASEC within 7 days according to HRO Art. 21¹.

5.5 Amendments

Substantial changes to the project set-up, the protocol and relevant project documents will be submitted to the Ethics Committee for approval according to HRO Art. 18 before implementation. Exceptions are measures that have to be taken immediately in order to protect the participants.

5.6 End of project

Upon project termination, the Ethics Committee is notified within 90 days. All data is anonymized upon termination of data analysis. Materials of water quality analysis and stool samples will be disinfected after analysis and disposed.

5.7 Insurance

Possible damages which are directly related to the study and are demonstrably the fault of Eawag, are covered by the liability insurance of Eawag (insurance policy 30/5.007.449) of the Baloise Insurance Ltd.

6 FURTHER ASPECTS

6.1 Overall ethical considerations

Children below the age of 5 are particularly vulnerable for diarrhoea related morbidity and mortality. The implementation of well-designed and effective programs to improve water supply, drinking water quality, hygiene and sanitation and establish the corresponding behavior effectively therefore is important to realize significant health gains.

Our study will evaluate the effectiveness of two different strategies aiming at providing participating households safe drinking water and it will assess the effectiveness of a WASH training program. Insights gained during the study will contribute to improving the quality and impact such interventions and therewith benefit future recipients of such programs.

The input required from participating caretakers and children is minimal - limited to time during the interview corresponding to less than 1 hour and to providing health data. The health measurements of children will not require more than 15 Minutes and will not expose children to any risks.

Participating household do not receive any financial benefit. However all households in the study area will benefit from the impact of the intervention with improved water supply and drinking water quality as well as improved hygiene. Also the control area will receive a water quality intervention after the completion of data collection. Households that participated in the study (in the intervention areas as well as in the control area) will be informed about the result of their examination and those found infected with parasites will be treated respective of their infection and at recommended doses following standard treatment schemes according to WHO. Similarly, adequate treatment and referral will be done for the nutritional deficiencies.

-

¹ A serious event is defined as any adverse event where it cannot be excluded, that the event is attributable to the sampling of biological material or the collection of health-related personal data, and which:

a. requires inpatient treatment not envisaged in the protocol or extends a current hospital stay;

b. results in permanent or significant incapacity or disability; or

c. is life-threatening or results in death.

The local authorities will be consulted about the aim and procedures of the study and their support will be solicited. All study participants will be given detailed information about the purpose of the study, the extent of their involvement and their right to be treated free of charge if found with any parasitic infection will be warranted. Informed and written consent will be obtained from all study participants. It will be pointed out that participation is voluntary and that the individuals may withdraw from the study at any time without further obligation.

6.2 Risk-Benefit Assessment

See above chapter 6.1.

6.3 Rationale for the inclusion of vulnerable participants

Children will be involved in the study because they are particularly sensitive to and affected by diarrhoea related morbidity and mortality. A study hypothesis therefore is, that particularly children below the age of 5 will experience the greatest health benefits from an intervention focusing on water safety and improved hygiene and health. Their health related indicators need to be assessed to confirm the hypothesis and evaluate the impact of the study on children's health. The collection of health data will not expose children to any risk.

Children's caretakers will be well informed about the purpose of the study and the methodology. Data will only be collected in households where children's caretakers have provided written informed consent. Participating children will be orally informed about the study and the purpose of the health measurements. They will be gently informed about the process of measurements before starting the examination.

7 QUALITY CONTROL AND DATA PROTECTION

7.1 Quality measures

All the enumerators will be trained on interviewing skills, questionnaire content, data quality and ethical conduct of human research. The co-principle investigator will assume the role of the supervisor during data collection in the field and will facilitate the field work during data collection and control quality of the data by auditing regularly. Interviewers and data collection assistants will contact the supervisor for any problem they faced during data collection and will keep the records of progress and problems/challenges faced during data collection process. Data quality will be ensured and will be cross checked regularly using a check file as well as for internal and external consistency. Laboratory investigation and anthropometric measurements will be revised after pre-test as per the need. Source data will be recorded digitally to avoid mistakes during manual data entry.

For quality assurance the questionnaire will be initially drafted in English, then translated into Nepali and back translation will be done to assure quality. The questionnaire will be pretested in a similar setting to identify required improvements, appropriateness, comprehensibility of questions and content validity.

Water quality analysis will include a random 10% double testing, each day, a negative control will be conducted by each team. The analysis of stool sample will involve a 5% random reprocessing of samples.

For quality assurance the Ethics Committee may visit the research sites. Direct access to the source data and all project related files and documents must be granted on such occasions.

7.2 Data recording and source data

Source data will be digitally recorded on tablets via ODK and will be electronically transferred for data analysis through SPSS or STATA. Source data comprises: data from household interviews and structured observations, results of water quality analysis, results of stool sample analysis, anthropometric measurements, results of finger prick test, results of clinical examination of children.

7.3 Confidentiality and coding

Project data will be handled with uttermost discretion and is only accessible to authorized personnel who require the data to fulfill their duties within the scope of the research project. On the CRFs and other project specific documents, participants are only identified by a unique participant number.

All personal data will be coded. Codes will be used for the labeling of water samples and stool samples and health data. Household's GPS data will be collected to identify households for the second panel of data collection. The participant identification list and GPS information will be stored by the principal investigator. Access to anonymized digital data will be restricted to researchers analyzing data by password protection. Back-ups of password protected files will be stored on external hard-drives.

Only anonymized data will be used for data analysis and to communicate study results.

Water quality & Stool samples will not identified by participant name but by a unique participant number. Samples will appropriately stored in a restricted area only accessible to authorized personnel. Samples and materials required for the analysis will be disinfected after the analysis and disposed.

7.4 Retention and destruction of study data and biological material

Study data will be archived for at least 10 years after study end. Water samples and stool samples will be disinfected and disposed directly after analysis.

8 FUNDING / PUBLICATION / DECLARATION OF INTEREST

There is no conflict of interest. The study will be funded by Eawag.

